8.2 Recording of Adverse Events

At each contact with the subject, the investigator must seek information on adverse events by specific questioning and, as appropriate, by examination. Information on all adverse events should be recorded immediately in the source document, and also in the appropriate adverse event section of the case report form (CRF). All clearly related signs, symptoms, and abnormal diagnostic, laboratory or procedure results should be recorded in the source document.

All adverse events occurring during the study period must be recorded. The clinical course of each event should be followed until resolution, stabilization, or until it has been ultimately determined that the study treatment or participation is not the probable cause. Serious adverse events that are still ongoing at the end of the study period must be followed up, to determine the final outcome. Any serious adverse event that occurs after the study period and is considered to be at least possibly related to the study treatment or study participation should be recorded and reported immediately.

Adverse events will be monitored and recorded during the four month postoperative time period.

8.3 Reporting of Serious Adverse Events and Unanticipated Problems

When an adverse event has been identified, the study team will take appropriate action necessary to protect the study participant and then complete the Study Adverse Event form and log. The sponsor-investigator will evaluate the event and determine the necessary follow-up and reporting required.

8.3.1 Sponsor-Investigator reporting, notifying the Mayo IRB

When an adverse event has been identified, the study team will take appropriate action necessary to protect the study participant and then complete the Study Adverse Event form and log. The sponsor-investigator will evaluate the event and determine the necessary follow-up and reporting required.

The sponsor-investigator will report to the Mayo IRB any UPIRTSOs and Non-UPIRTSOs according to the Mayo IRB Policy and Procedures.

Any serious adverse event (SAE) must be reported to the Mayo IRB as soon as possible but no later than 5 calendar days. The adverse event report will contain the following information:

Fields populated from the clinical research database:

- Subject's name
- Medical record number

- Disease/histology (if applicable)
- Protocol number

Data needing to be entered:

- The date the adverse event occurred
- The adverse event
- Relationship of the adverse event to the treatment (drug, device, or intervention)
- If the adverse event was expected
- The severity of the adverse event
- The intervention

The PI's signature and the date it was signed are required on the completed report. For this protocol, only directly related SAE's will be reported to the IRB.

8.3.2 Sponsor-Investigator reporting: Notifying the FDA

The sponsor-investigator will report to the FDA all unexpected, serious suspected adverse reactions according to the required IND Safety Reporting timelines, formats and requirements.

Unexpected fatal or life threatening suspected adverse reactions where there is evidence to suggest a causal relationship between the study drug/placebo and the adverse event, will be reported as a serious suspected adverse reaction. This will be reported to the FDA on FDA Form 3500A, no later than 7 calendar days after the sponsor-investigator's initial receipt of the information about the event.

Other unexpected serious suspected adverse reactions where there is evidence to suggest a causal relationship between the study drug/placebo and the adverse event, will be reported as a serious suspected adverse reaction. This will be reported to the FDA on FDA Form 3500A, no later than 15 calendar days after the sponsor-investigator's initial receipt of the information about the event.

Any clinically important increase in the rate of serious suspected adverse reactions over those listed in the protocol or product insert will be reported as a serious suspected adverse reaction. This will be reported to the FDA on FDA Form 3500A no later than 15 calendar days after the sponsor-investigator's initial receipt of the information about the event.

Findings from other studies in human or animals that suggest a significant risk in humans exposed to the drug will be reported. This will be reported to the FDA on FDA Form 3500A, no later than 15 calendar days after the sponsor-investigator's initial receipt of the information about the event.

8.4 Unblinding Procedures

In case of an adverse event, un-blinding of the study participant will be carried out immediately. The event will be analyzed in the same manner as any severe adverse drug reaction. This will be reported to the appropriate agencies with the analysis, conclusions and recommendations. The study will then

be re-instituted if given approval to continue. This study subject will be categorized as a treatment failure and imputed the most negative score on all outcomes.

All serious adverse events (SAE) will be reported, and un-blinding will be part of managing an SAE. The PI and the research team will continually review blinded data after each subject has study interaction, including a review of all adverse events, to determine seriousness and relation to study drug. Minor adverse events and unusual complications encountered during the period of tissue expansion will be carefully recorded. In the event of a serious adverse reaction to the treatment, the study participant will be treated accordingly depending on the reaction.

Any AE that occurs during the course of the study will be disclosed to the Mayo Clinic IRB. All SAE will be reported to the FDA as well as to Allergan within 15 calendar days after its first knowledge. The Principal Investigator will provide written notice to Allergan within 15 calendar days of any occurrence(s) of either (i) pregnancy or (ii) lactation during the time period of effect of BOTOX®, which can last three to four months.

In cases where un-blinding was not associated with an SAE, such actions will be reported in a timely manner. Notification of sponsor will be performed within 24 hours by phone or fax, followed by a written narrative of the event within 48 hours. The statistician conducting the interim analysis will contact Research Pharmacy personnel to proceed with un-blinding not associated with an SAE.

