All unresolved adverse events should be followed by the investigator until the events are resolved, the subject is lost to follow-up, or the adverse event is otherwise explained. At the last scheduled visit, the local investigator should instruct each subject to report, to the local investigator, any subsequent event(s) that the subject, or the subject's personal physician, believes might reasonably be related to participation in this study. The local investigator should notify the study regulatory sponsor of any death or adverse event occurring at any time after a subject has discontinued or terminated study participation that may reasonably be related to this study. The sponsor should also be notified if the local investigator should become aware of the development of problems, cancer or of a congenital anomaly in a subsequently conceived offspring of a subject that has participated in this study.

Hospitalization, Prolonged Hospitalization or Surgery

Any adverse event that results in hospitalization or prolonged hospitalization should be documented and evaluated for relationship to the study drug/placebo. If there is a reasonable possibility that it is related to the study drug/placebo then will be reported as a serious adverse event unless specifically instructed otherwise in this protocol. Any condition responsible for surgery should be documented as an adverse event if the condition meets the criteria for an adverse event.

Neither the condition, hospitalization, prolonged hospitalization, nor surgery are reported as an adverse event in the following circumstances:

- Hospitalization or prolonged hospitalization for diagnostic or elective surgical procedures for a preexisting condition. Surgery should **not** be reported as an outcome of an adverse event if the purpose of the surgery was elective or diagnostic and the outcome was uneventful.
- Hospitalization or prolonged hospitalization required to allow efficacy measurement for the study.
- Hospitalization or prolonged hospitalization for therapy of the target disease of the study, unless it is a worsening or increase in frequency of hospital admissions as judged by the clinical investigator.

The expected adverse events from surgery include post-operative pain, nausea, vomiting, general anesthesia risks, hemorrhage, surgical site infection, mastectomy skin necrosis, seroma, surgical site paresthesia.

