8.5 Stopping Rules

The study will be stopped immediately if any patient suffers *at least one* of the following events during the course of the study, unless it can be shown that this event was unrelated to participation in the clinical trial:

- 1) Death
- 2) Upper limb paralysis or weakness
- 3) Bulbar weakness
 - a. Blurred vision
 - b. Facial paralysis
 - c. Dysarthria
- 4) Anaphylactic reaction
- 5) Any severe adverse drug reaction

The study will be stopped if the absolute difference in the surgical site infection (SSI) rate is 15% higher in one treatment group as compared to the other treatment group. The study statistician will compare the SSI rates in a blinded fashion on a periodic basis and notify the Principle Investigator of this information. The study team will review the data and notify the DSMB accordingly.

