8.6.2 Independent Data and Safety Monitoring Board

Data Safety and Monitoring Board (DSMB): An independent Data Safety and Monitoring Board will consist of [name], [name], [name], [name], [name], [name] and a Mayo Clinic statistician who is not involved with this project. The Data Safety Monitoring Board will assess safety and efficacy at interim analysis (when 75 patients have been enrolled). The Board will be empowered to recommend continuation, modification, or early closure of the trial. Recommendations of the Data Safety Monitoring Board will be reviewed by the Steering Committee who will make the final decision to terminate accrual early. In addition, patient safety will be protected by open communication and reporting of patient safety concerns by any personnel involved in the study to the principal investigator or Trial Steering Committee members during the course of patient participation in the study. If significant issues arise they will be reported to both institutional IRBs for further consideration.

9 Data Handling and Record Keeping

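### Sections 8.4 and 8.5 conflict on which events interrupt the whole study and on whether and how it resumes, and neither is tied to the decision authority in 8.6.2

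*Combined protocol and SAP*

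**What the plan says.** Three places in the combined protocol and SAP bear on interrupting the study as a whole.

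- **Section 8.4 (Unblinding Procedures), first paragraph.** It opens: "In case of an adverse event, un-blinding of the study participant will be carried out immediately". It continues: "The event will be analyzed in the same manner as any severe adverse drug reaction". After reporting to the appropriate agencies, the study will then "be re-instituted if given approval to continue".
- **Section 8.4, second paragraph.** Unblinding is described as part of managing a serious adverse event, and blinded data are reviewed continually for seriousness and relation to study drug. For lesser events: "Minor adverse events and unusual complications encountered during the period of tissue expansion will be carefully recorded".
- **Section 8.5 (Stopping Rules).** "The study will be stopped immediately if any patient suffers" one of five listed event types, the last being "Any severe adverse drug reaction". Events shown to be unrelated to participation are exempt. A separate rule stops the study when SSI rates differ by 15% in absolute terms between arms. There the statistician informs the principal investigator, and the study team reviews the data and notifies the DSMB.
- **Section 8.6.2 (DSMB).** The Board may recommend continuing, modifying or closing the trial. Its recommendations "will be reviewed by the Steering Committee who will make the final decision to terminate accrual early".

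Section 8.1 supplies the context for the word adverse event: "The expected adverse events from surgery include post-operative pain, nausea, vomiting", and the list goes on to include surgical site infection and seroma.

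**The concern.** A study can be re-instituted only if it has been halted. The first paragraph of 8.4 therefore implies that the study is suspended after an adverse event, and it does not limit this to serious, related or listed events. Section 8.5 sets a much narrower trigger and an exemption that 8.4 lacks. Neither section refers to the other, and neither says how it fits with the decision route in 8.6.2.

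The text that staff follow decides whether randomisation stops, whether it can restart and who may restart it. This is not remote. Section 3.4 names unintended weakness of the injected or nearby muscles as a possible side effect and counsels women about loss of strength and blurred vision. Upper limb weakness and blurred vision are both on the 8.5 list. One such report would raise the restart question at once, and one routine surgical event would raise the trigger question.

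**Working it through.** No stated figure decides this point, so the check is a comparison of the texts.

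| Question | 8.4 | 8.5 | 8.6.2 |
|---|---|---|---|
| What triggers it? | An adverse event, not further limited (para 1); minor events only recorded (para 2) | Five listed event types, or a 15% absolute SSI difference | Not event-triggered; follows DSMB advice |
| Exempt if unrelated? | No exemption stated | Yes, for the listed events | Not addressed |
| What happens? | A halt is implied, followed by restart | Immediate stop for listed events; a stop for the SSI difference; neither called temporary or permanent | Possible early end of accrual |
| How does it resume? | On approval | Not stated | Not stated |
| Who decides? | Approver not named | No one named to judge relatedness or lift a stop | Steering Committee, on ending accrual early |

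Four test events show where the texts part:

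1. **Seroma (unlisted, expected under 8.1).** First paragraph of 8.4: implied halt and restart. Second paragraph of 8.4, if the event is minor: recorded only. 8.5: no stop. Outcome: no halt, or an implied pause.
2. **Upper limb weakness not shown to be unrelated (listed).** 8.5: immediate stop, no restart route given. 8.4: restart on approval. Outcome: a stop, with or without a way back.
3. **A listed event shown to be unrelated.** 8.5: no stop. 8.4: no exemption, so a halt is still implied.
4. **SSI difference reaching 15%.** 8.5: the study is stopped, but the steps described are review and notification. No text says who orders or lifts the stop. 8.4 and 8.6.2 do not mention it.

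**Illustration of scale (assumed rates only).** Let a share p of the 134 planned women have at least one adverse event, with one halt per woman.

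- Expected triggers of 8.4 read literally = 134 × p: 134 × 0.05 = 6.7; 134 × 0.10 = 13.4; 134 × 0.30 = 40.2.
- Chance of at least one trigger among 134 = 1 − (1 − p)^134: 74% at p = 1% and 99.9% at p = 5%.
- If each restart took 2 to 4 weeks without overlap (also assumed), time lost = 134 × p × (2 to 4): 13 to 27 weeks at 5%, 27 to 54 at 10% and 80 to 161 at 30%. The planned 40 months of accrual is about 174 weeks.
- For 8.5, if a listed event not shown to be unrelated occurred in 0.2%, 0.5% or 1% of women, the chance of at least one among 134 is 1 − 0.998^134 = 24%, 1 − 0.995^134 = 49% or 1 − 0.99^134 = 74%.

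**The case against.** The strongest reply is that the sections are complementary. Section 8.4 is headed as an unblinding procedure and never orders a halt. It mentions severe adverse drug reactions, which is also the last item in 8.5, and then describes restarting. It could be the restart step after an 8.5 stop, with approval coming from the agencies to which the event was reported. Its second paragraph suggests that the authors did not mean every minor event to halt the trial.

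Part of this stands. The halt in 8.4 is implied and not stated, and the complementary reading may be what was intended. But nothing in the text says so, the triggers do not match, and the exemption appears in one section only. The agencies are not named as approvers. Nor is the IRB an obvious default: 8.3.1 restricts reporting to it to directly related serious events, while 8.4 discloses any adverse event to it.

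Some stronger readings are tempting and should be set aside:

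- **Three rival halting rules.** Section 8.6.2 says who acts on DSMB advice. It is a decision authority and can stand beside 8.5; what is missing is the link.
- **The same event could mean no halt, a pause or the end of the trial.** Section 8.5 never says that a stop is permanent, and no single event receives all three outcomes.
- **Section 8.4 classes every adverse event as a severe reaction.** It says how the event is analysed, not how it is classified.
- **The target of 128 complete data sets would be missed.** This depends on assumed rates and delays, and section 7.1 allows enrolment to be extended.

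**Conclusion.** The contradiction is real, in limited form. For an unlisted event, or a listed event shown to be unrelated, 8.4 read literally and 8.5 cannot both be followed. For a listed event not shown to be unrelated, 8.5 requires a stop and leaves open whether it is a pause or a termination, while only 8.4 describes a restart, on the approval of an unnamed body. Section 8.6.2 does not say whether the Steering Committee can lift or override an 8.5 stop, and the SSI rule has the same gap.

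This conclusion rests on the wording alone. The counts of about 7 to 40 triggers and the weeks lost rest on assumed event rates, assumed approval times and the literal reading of 8.4, which its own second paragraph undercuts. They show that the choice of reading matters; they do not forecast accrual. The matter should be corrected because it governs randomisation and the response to a safety event. The documents do not settle which rule is right, and no view on that is offered here.

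**What to change.** Reconcile 8.4, 8.5 (including the SSI rule) and 8.6.2 so that one text states:

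- which events interrupt the whole study;
- whether the exemption for unrelated events applies;
- whether each interruption is a pause or a termination;
- which body approves a restart.

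The other sections should then refer to that text. The content of each item, including which events qualify and who holds the authority, is for the sponsor and the DSMB to decide.

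The cost is wording in three sections and a protocol amendment, which section 11 requires to go to the IRB for formal approval. It needs no extra patients, visits or data collection.

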8.1 Definitions

Adverse Event: An untoward or undesirable experience associated with the use of a medical product (i.e. drug, device, biologic) in a patient or research subject.

Note: An adverse event (also referred to as an adverse experience) can be any unfavorable and unintended sign (e.g., an abnormal laboratory finding), symptom, or disease temporally associated with the use of a drug, without any judgment about causality. An adverse event can arise from any use of the drug (e.g., off-label use, use in combination with another drug) and from any route of administration, formulation, or dose, including an overdose.

Suspected Adverse Reaction: Suspected adverse reaction means any adverse event for which there is a reasonable possibility that the drug caused the adverse event. For the purposes of IND safety reporting, 'reasonable possibility' means there is evidence to suggest a causal relationship between the drug and the adverse event. A suspected adverse reaction implies a lesser degree of certainty about causality than adverse reaction, which means any adverse event caused by a drug.

Reasonable Possibility: There is evidence to suggest a causal relationship between the drug and the adverse event.

Serious: An adverse event or suspected adverse reaction is considered "serious" if, in the view of either the investigator or sponsor, it results in any of the following outcomes: Death, a life-threatening adverse event, inpatient hospitalization or prolongation of existing hospitalization, a persistent or significant incapacity or substantial disruption of the ability to conduct normal life functions, or a congenital anomaly/birth defect. Important medical events that may not result in death, be life-threatening, or require hospitalization may be considered serious when, based upon appropriate medical judgment, they may jeopardize the patient or subject and may require medical or surgical intervention to prevent one of the outcomes listed in this definition. Examples of such medical events include allergic bronchospasm requiring intensive treatment in an emergency room or at home, blood dyscrasias or convulsions that do not result in inpatient hospitalization, or the development of drug dependency or drug abuse.

Unanticipated Problems Involving Risk to Subjects or Others (UPIRTSO)

Any unanticipated problem or adverse event that meets the following three criteria:

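### Section 8.4 ties unblinding and worst-score imputation to any adverse event; the narrower trigger it probably intends is not named, and Section 7 does not carry the rule

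*Combined protocol and SAP*

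**What the plan says.** The first paragraph of Section 8.4 gives the trigger: "In case of an adverse event, un-blinding of the study participant will be carried out immediately". It then says that the event is analysed like a severe adverse drug reaction and reported, and that the study is re-instituted if approval is given. It closes with the consequence for the data: "This study subject will be categorized as a treatment failure and imputed the most negative score on all outcomes".

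The second paragraph of 8.4 reads differently. It says that "un-blinding will be part of managing an SAE", that the research team will "continually review blinded data after each subject has study interaction, including a review of all adverse events", and that "Minor adverse events and unusual complications encountered during the period of tissue expansion will be carefully recorded". The last paragraph provides for unblinding not linked to an SAE, carried out through the statistician who does the interim analysis.

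Section 8.1 defines an adverse event broadly, as any unfavourable sign, "symptom, or disease temporally associated with the use of a drug, without any judgment about causality". It adds: "The expected adverse events from surgery include post-operative pain, nausea, vomiting", followed by infection, seroma and other surgical events.

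Sections 7.1 (sample size), 7.2 (methods and missing data) and 7.3 (analysis population) do not mention the treatment-failure rule.

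**The concern.** The two primary outcomes, NPIS pain and BREAST-Q physical well-being, are reported by the patient, so they depend on the blind. A trigger that covers any adverse event would unblind women for ordinary effects of a mastectomy. It would also replace their recorded pain scores with the worst possible one. Post-operative pain, which the trial sets out to measure, could itself set off that replacement.

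If a narrower event was meant, the reader still cannot tell whether it is any SAE, a drug-related SAE or a severe drug reaction. These differ. Section 8.5 halts the study for its listed events "unless it can be shown that this event was unrelated to participation in the clinical trial", so an SAE shown to be unrelated would not stop the trial but could still trigger 8.4.

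The text also leaves open whether scores recorded before the event are replaced, and whether the imputed value is the scale limit or the worst score observed. Section 7 is silent, so these choices could be made once results are known.

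**Working it through.** **1. The wording, set side by side**

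| Place | Event covered | Consequence |
|---|---|---|
| 8.4, paragraph 1, opening | any adverse event | immediate unblinding |
| 8.4, paragraph 1, middle | handled like a severe drug reaction; study re-instituted if approved | implies the study had been halted |
| 8.4, paragraph 1, end | the same woman | treatment failure, worst score on all outcomes |
| 8.4, paragraph 2 | SAE | unblinding is part of its management |
| 8.4, paragraph 2 | all adverse events | reviewed on blinded data |
| 8.4, paragraph 2 | minor events | recorded |
| 7.1 to 7.3 | none | rule absent |

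A team cannot unblind at every adverse event and also keep reviewing all adverse events blinded. The text does not say which instruction prevails.

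**2. The plan's own figure**

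Inputs from 7.1: means 4.0 and 3.0, SD 2.0, significance level 0.05 (two-sided assumed), 80% power, two-sample t-test. The noncentral t calculation gives 64 per group with power 80.1%, as stated. The normal approximation gives 63. The sample size arithmetic is sound, but it makes no allowance for imputed worst scores.

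**3. Effect of the rule on the difference**

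Assumptions, because the documents give no event rate and the NPIS appendix is not shown: worst score 10 (the 0 to 10 range is that of the retrospective study cited in 7.1), one pain score per woman, 64 per arm. With *a* placebo women and *b* BTX-A women set to 10:

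difference = 1.0 + *a*(10 − 4)/64 − *b*(10 − 3)/64

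- One per arm: 1.0 + 6/64 − 7/64 = 0.98
- BTX-A only, one: 1.0 − 7/64 = 0.89
- BTX-A only, two: 1.0 − 14/64 = 0.78
- BTX-A only, three: 1.0 − 21/64 = 0.67
- Six per arm: 1.0 + 36/64 − 42/64 = 0.91

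**4. Effect on the SD and on power**

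If a share *q* of an arm with mean μ is set to 10, its variance is about (1 − *q*) × 2.0² + *q*(1 − *q*)(10 − μ)². For three BTX-A women, *q* = 3/64 = 0.047 and μ = 3, so the variance is 0.953 × 4 + 0.047 × 0.953 × 49 = 6.00. The placebo variance stays at 4.0, and the pooled SD is √((4.00 + 6.00)/2) = 2.24.

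Power was simulated with normal scores, fixed event counts, a two-sided t-test and 40,000 runs per case. Entering the difference and pooled SD in the noncentral t formula serves as a check.

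| Women set to 10 | Difference | Power, simulated | Power, formula |
|---|---|---|---|
| none | 1.00 | 80% | 80% |
| 1 per arm | 0.98 | about 75% | 73% |
| 1 on BTX-A | 0.89 | about 68% | 67% |
| 2 on BTX-A | 0.78 | about 53% | 53% |
| 3 on BTX-A | 0.67 | about 38% | 39% |
| 6 per arm (broad trigger) | 0.91 | about 45% | 47% |

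The two methods agree within about 2 percentage points. With the Wilcoxon test, which 7.2 also allows, the loss is smaller: 79% with no events, then 72%, 65% and 57% for one, two and three BTX-A women.

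**The case against.** The strongest reply is that a severe event was plainly meant. A study can be re-instituted only if it was halted, and 8.5 halts it for a severe drug reaction, not for nausea. Counting such a reaction as failure with the worst score is a legitimate pre-specified approach, and conservative for the drug. On that reading few women are affected, and two or three drug-related events would imply repeated halts. The illustration also uses the lowest of the plan's three SDs, and its larger losses at small counts put every event on BTX-A.

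Much of this stands. The narrow intent is likely, the figures are illustrative, and the treatment-failure approach is the sponsor's to choose. But the operative sentence still says any adverse event, several different narrow events would fit the remaining text, and neither the imputed score nor its timing is defined.

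A reader might infer that 8.4 elsewhere limits unblinding to serious events. It does not: it never says so, and its last paragraph provides for unblinding unconnected with an SAE. A reader might also see a contradiction with the zero-value method in 7.2, which would give the best pain score where 8.4 gives the worst. That method is one of several listed for missing data, whereas a woman under 8.4 already has an assigned score. Whether zero-value imputation is sensible is a separate question.

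**Conclusion.** The rule is wrong as written. Followed literally, it would unblind women and overwrite primary outcome scores for events that surgery itself is expected to cause. The surrounding text points to something narrower without naming it, and the statistical section does not carry the rule.

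Under the stated assumptions, one affected woman per arm costs about 5 percentage points of power (80% to about 75%). One to three on BTX-A only reduce power to about 68%, 53% or 38%, and six per arm to about 45%. These figures rest on assumed event counts, a worst score of 10, SD 2.0 and a t-test on one score per woman.

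It would be tempting to conclude that the rule could produce a false claim of efficacy. The documents do not support that. Section 3.4 names unintended muscle weakness as a BTX-A effect. If drug-related events fall mainly in that arm, the rule works against BTX-A, and the risk is a missed or diluted benefit. Nor do the documents show that most women would in practice be unblinded; that follows only from the literal trigger, which was probably not intended. The point should be fixed before the data are analysed, but it does not undermine the design.

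**What to change.** In Section 8.4:

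- Limit emergency unblinding to serious adverse events where knowing the assignment affects care.
- Limit the treatment-failure rule to one named event, for example a serious suspected drug reaction, judged before unblinding.
- State that other adverse events neither break the blind nor trigger imputation.
- Define the imputed score as the scale limit, applied only to assessments after the event and not to outcomes fixed at surgery, such as initial percent volume expansion.

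In Section 7.2, cross-refer to the rule and add an analysis of observed scores as a sensitivity analysis.

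Making observed scores the primary analysis, with worst-score imputation as the sensitivity analysis, is an option for the sponsor. It changes what the primary comparison measures, because the pain score would no longer penalise severe reactions, so the defect does not require it.

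The cost is a small wording change and one extra analysis, with no added patients, visits or data.
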